3.0 Intervention to be studied

Emerging evidence suggests that resistance training is effective at reducing depressive symptoms.^{11,12,27} We developed an innovative rehabilitation approach, Post-stroke Optimization of Walking using Explosive Resistance (POWER) training; a high-velocity, high-intensity lower extremity resistance training intervention that improves post-stroke muscular and locomotor function (RR&D RX000844).¹³ Preliminary findings from this study suggest POWER training reduces symptoms in those with mild to moderate depression (Figure 1). We seek to build upon these findings to determine its efficacy (vs. control) in treating PSD.

Chronic stroke survivors with mild to moderate depression (n=32) will be randomly assigned to the intervention (POWER) or attention control (stretching) group. POWER training will take place over a 12-week period (3 sessions/week) with exercises including leg press, calf raises, and jump training, all performed at high concentric velocity, as well as trials of fast walking. We will perform bi-weekly measurements of depressive severity using the Hamilton Rating Scale for Depression (HRSD).

Chronic stroke survivors with mild to moderate depression (n=16) as well as age (± 5 yrs), gender and severity-matched (determined by walking speed) non-depressed stroke subjects (n=16) will complete 12 weeks of POWER training. We will perform bi-weekly HRSD measurements as well as comprehensive dynamometric assessments of paretic and non-paretic knee extensor muscle power generation and self-selected walking speed at these same time points. Secondary assessments of locomotor function will be the six-minute walk test (6MWT) and the amount of community walking measured via step activity monitors (SAM).

Stretching is being used as an attention control condition for POWER training. Control subjects will participate in a stretching protocol for the same duration (i.e. 60 minutes per session) and frequency (3 days per week) for 12 weeks to ensure that they have equal interaction with the study staff and controlling for the effects of repeated social interaction on depressive symptoms.

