12.0 Data Management

Data Analysis Plan: We will compare the effects of POWER training (vs. control) on HRSD scores. We will also determine response ($\geq 50\%$ reduction in symptoms) and remission ($\text{HRSD} < 10$) rates following training and at a six-month follow-up. We will utilize repeated measures mixed effects models to assess significant changes in outcomes between groups. Time and group will serve as dependent variables, as well as their interactions. A random intercept term will be included in the model to account for clustering within subjects. Various error structures associated with the repeated measures will be considered (e.g. compound symmetry vs. auto-regressive).

We will determine if PSD limits response to treatment by making between group comparisons of change (post-pre) in outcomes in depressed vs. non-depressed subjects utilizing repeated measures mixed models. Time (seven occasions), group (depressed vs. non-depressed) and their interaction will serve as dependent variables. Three primary dependent variables of interest here are, self-selected walking speed (SSWS) and paretic leg power generation. A random intercept term will be included in the model to account for clustering within subjects. Various error structures associated with the repeated measures over time will be considered (e.g. compound symmetry vs. auto-regressive). Analyses incorporating differences in outcomes as dependent variables will examine whether changes over time are more pronounced in depressed versus non-depressed subjects as well as whether changes are more pronounced in depressed subjects with the greatest improvement in HRSD. These models will also incorporate random subject effects to account for within-subject dependence. To determine associations between changes in outcomes, we will look at the relationships between outcomes using Pearson or Spearman correlations, depending on the distribution of the data. Further, we will use segmented (joint-point) regression to estimate if specific thresholds exist that mark in individual subjects where HRSD starts improving (decreases) and other outcomes start to improve (increase) to help us understand

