Sample size determination and Statistical Approach: A total of 50 post-stroke subjects will be recruited. For Aim 1, 32 subjects with PSD will participate in either POWER training or control intervention (n=16 per group). These analyses will rely on longitudinal measures and we assume (based on experience with this intervention) that no more than 15% will fail to complete all assessments. This is an extremely conservative approach in that none of the subjects in our pilot trial withdrew from treatment. With 16 subjects enrolled per group and a 15% attrition rate over time (resulting in complete data on 13 subjects per group), we would have at least 80% power to detect a minimum difference in the change in HRSD from baseline to the end of the study of 2.94 (change in pilot data = 6.6) with a s.d. of 5.3 (at 5% significance level). Since this is a longitudinal study, we also incorporated an autocorrelation (AR(1)) of 0.5 for 10 measurements within individuals. The published studies report treatment effect sizes ranging from 0.6 to 0.9, which are more conservative. In our preliminary data, we observed an effect size of 1.19 (95% CI 0.98 to 1.36) for improvement in depression severity. To detect this effect we will have more than 90% power. For Aim 2, with baseline data from n=26 subjects, we will have 80% power to detect a minimum difference (pre-post) of 0.13 m/s for SSWS (s.d. = 0.2 m/s) and 17.88 ft/lb for muscle strength (s.d.=31.9 ft/lb) using a longitudinal approach with an autocorrelation (AR (1)) of 0.5 for 10 measurements within individuals. In the statistical analysis for both aims, we will summarize the longitudinal data using Spaghetti plots. If the spaghetti plots suggest linear or quadratic trend we will include these in the model along with appropriate interactions and random effects. We will perform appropriate model diagnostics and, if needed, consider transformations to achieve normality. To reduce potential heterogeneity in the data, secondary analysis will adjust for covariates such as depression level.

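### Aim 2 matches on age, gender and walking speed, but its model uses none of the three, so intervals for the difference in change may be too wide

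*Combined protocol and SAP*

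**What the plan says.** Section 3.0 gives POWER training to both Aim 2 groups. One is 16 participants with mild to moderate depression; the other is described as "age (± 5 yrs), gender and severity-matched (determined by walking speed) non-depressed stroke subjects (n=16"). Age has a stated tolerance. Walking speed has none, and Section 5.0 admits speeds from 0.2 to 0.8 m/s. The text does not say whether matching is one-to-one or at group level.

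Section 12.0 sets the Aim 2 analysis as "making between group comparisons of change (post-pre) in outcomes in depressed vs. non-depressed subjects". Its terms are: "Time (seven occasions), group (depressed vs. non-depressed) and their interaction will serve as dependent variables". I read the word dependent there as a slip for predictor. The only random effect is at subject level: "A random intercept term will be included in the model to account for clustering within subjects". The named outcomes are "self-selected walking speed (SSWS) and paretic leg power generation".

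Adjustment appears in two places. Section 12.0 says "secondary analysis will adjust for covariates such as depression level". Section 13.0, under Data Quality Assurance, has the baseline balance between conditions inspected in case adjustment proves necessary. Neither names age, gender or walking speed.

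**The concern.** Depressed and non-depressed participants are not randomised to their groups, so matching is the main design protection against differences in age, gender and severity. An analysis that ignores the matching variables leaves in the error term whatever variation in change they explain. The precision that matching could have bought is then lost, in a comparison powered on 26 people.

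Matching is also only approximate. Differences can remain within five years of age and within an unstated walking-speed tolerance, and dropout can separate matched participants. Nothing in the planned primary model corrects for either.

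**Working it through.** **1. Does the power calculation use the matching?** Section 12.0 says "For Aim 2, with baseline data from n=26 subjects, we will have 80% power", with SD 31.9 ft/lb for strength, AR(1) correlation 0.5 and 10 measurements. I assume 13 per group and a two-sided 5% test. The variance factor for a mean of m AR(1) measurements is

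f = [1 + 2 Σ (1 − k/m) 0.5^k] / m, summed over k = 1 to m − 1, which is 0.260 for m = 10.

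For two independent groups, the detectable difference is (1.960 + 0.842) × 31.9 × √(2 × 0.260/13) = 17.88 ft/lb. The plan's figure reproduces exactly, with no allowance for matching. (For walking speed, the stated 0.13 m/s reproduces with 7 measurements, 0.1296, but not with 10, 0.112. That is a separate inconsistency.)

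**2. What is lost if matched participants respond alike?** Let ρ be the within-pair correlation of change. For pairs, the variance of the group difference is (1 − ρ) times the independent-groups value. So the correct standard error is √(1 − ρ) times the reported one, and the equivalent sample size is 1/(1 − ρ). The true error rate of the nominal 5% test is 2[1 − Φ(1.96/√(1 − ρ))]. The last column applies √(1 − ρ) to 17.88 ft/lb as an illustration of scale.

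| ρ (assumed) | Correct SE smaller by | Equivalent sample | True error of nominal 5% test | Detectable strength difference, ft/lb |
|---|---|---|---|---|
| 0 | 0% | 1.00 | 5.0% | 17.88 |
| 0.1 | 5% | 1.11 | 3.9% | 16.96 |
| 0.2 | 11% | 1.25 | 2.8% | 15.99 |
| 0.3 | 16% | 1.43 | 1.9% | 14.96 |
| 0.5 | 29% | 2.00 | 0.6% | 12.64 |

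**3. When is ρ for change above zero?** If matched participants share only a stable personal level, that level cancels from each person's change. In simulation the group-by-time test then kept its 5% error rate (4.9% to 5.1%). If they also share response, the test becomes conservative: 3.5% at a slope correlation of 0.3 and 2.5% at 0.5.

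**4. Walking speed.** Here the matched quantity is the measured baseline, which is itself part of the change score. Let r be the correlation between baseline and week 12, with equal variances and exact matching. Change has variance 2(1 − r), of which (1 − r)² comes from baseline, so ρ = (1 − r)²/[2(1 − r)] = (1 − r)/2.

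| r | ρ for change | Simulated error of the unpaired 5% test |
|---|---|---|
| 0.9 | 0.05 | 4.6% |
| 0.8 | 0.10 | 3.9% |
| 0.5 | 0.25 | 2.6% |
| 0.5⁶ = 0.016 (the plan's AR(1) at lag 6) | 0.49 | 0.8% |

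The last row is an upper end, because it treats baseline and week-12 speed as almost unrelated. A paired test stayed near 5% in every row.

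**5. Would a random matched-pair intercept recover the loss?** No. It adds the same constant to both members at every visit, so it drops out of each member's change. A generalised least squares check (13 pairs, 7 occasions, compound symmetry, total variance 1) gave a standard error of 0.351 for the week-12 change contrast, whether 0%, 30%, 50% or 80% of the between-subject variance was shared within pairs.

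**6. Dropout.** If the 15% attrition stated for Aim 1 applied independently to each member of 16 pairs (an assumption), 16 × 0.85² ≈ 11.6 pairs would stay complete and about 4 would break. The plan has no rule for these.

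**The case against.** A reader might infer that the planned error bars are simply wrong, or that the test gives too many false positives. The documents do not support that. With positive correlation the error runs the other way, and for change it vanishes when the matching factors do not predict change. No passage says that they do; Section 3.0 treats walking speed only as a marker of severity.

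A reader might also infer that a paired analysis is required. One-to-one pairing is suggested by the five-year age tolerance but never stated, and under group-level matching the √(1 − ρ) formula does not apply as written. With 13 pairs, a strictly paired t-test would also lose power if ρ is zero: 73% against 77% at 17.88 ft/lb.

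The plan is not silent on adjustment. Its list of covariates for secondary analysis is open, and it provides for a check of baseline balance. The mixed model keeps partial data, so dropout does not simply destroy balance. The figure of 13 per group is the Aim 1 figure; Aim 2 states only 26. Finally, the primary outcome is HRSD change, so this is not the trial's main comparison.

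All of this limits the size of the point. What remains is that no matching variable is named for any primary Aim 2 model, and the adjustment on offer is secondary or decided after looking at the data.

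**Conclusion.** The point holds as a matter of efficiency and pre-specification. The Aim 2 model and power calculation both ignore the variables on which the groups are matched. If those variables predict change, the intervals for the difference in change are too wide by an amount the documents cannot fix: the correct standard error is 0% to 29% smaller for assumed within-pair correlations of 0 to 0.5. Zero belongs in that range. Walking speed is the outcome most likely to be affected; for leg power the effect depends on how well age, gender and walking speed predict change.

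The conservative direction concerns precision only. Residual imbalance in a non-randomised comparison could move the estimate either way, and the documents give no basis for a figure. None of this supports a claim of inflated false positives or an invalid Aim 2 analysis.

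**What to change.** In Section 12.0:

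- Pre-specify age, gender and baseline self-selected walking speed as covariates in the primary Aim 2 between-group models.
- Where baseline stays among the modelled occasions, give each covariate a linear interaction with time, since a main effect alone does little for a change contrast. In a model of change, main effects are enough.
- For the walking-speed outcome, model post-baseline values or change with baseline speed as the covariate, so that baseline speed is not on both sides.
- Do not rely on a random matched-pair intercept instead; it does not sharpen the group-by-time contrast.
- State whether matching is one-to-one and what walking-speed tolerance applies. Covariate adjustment works under either type of matching and when one member of a pair drops out.

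The change is to wording only, because the variables are already needed for matching. It costs about three degrees of freedom in a model of change or with main effects only, and about six with linear-time interactions. Full interactions with seven-level time would need 3 + 3 × 6 = 21 parameters on 26 to 32 people and should be avoided. If the covariates turn out not to predict change, the price is a small loss of power.

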5.0 Inclusion and Exclusion Criteria/ Study Population

Subjects (male and female), ages 18-85, will be screened and recruited for the study 6-60 months following stroke. The pool of post-stroke candidates for the study will be recruited through the extensive recruiting mechanisms at the local VAMC as well as the Clinical and Translation Tools and Resources CTTR core at MUSC. All participants will have had a new ischemic stroke.

Inclusion criteria will be: 1) age 18-85; 2) stroke at least 6 months prior, 3) residual paresis in the lower extremity (Fugl-Meyer LE motor score <34); 4) ability to walk without assistance and without an AFO during testing and training at speeds ranging from 0.2-0.8 m/s; 5) no antidepressant medications or no change in doses of psychotropic medication for at least 4 weeks prior to the study (6 weeks if newly initiated medication); 6) HRSD question #9 regarding suicide <2; and 7) provision of informed consent. In addition, depressed subjects will screen for probable major depressive disorder (PHQ-9 > 10) and be diagnosed using the Structured Clinical Interview for Depression (SCID) according to the Diagnostic and Statistical Manual of Mental Disorders, Fourth Edition (DSM-IV). All subjects who meet criteria for training must complete an exercise tolerance test and be cleared for participation by the study physician.

Exclusion criteria will be: 1) Unable to ambulate at least 150 feet prior to stroke, or experienced intermittent claudication while walking; 2) history of congestive heart failure, unstable cardiac arrhythmias, hypertrophic cardiomyopathy, severe aortic stenosis, angina or dyspnea at rest or during ADL's; 3) History of COPD or oxygen dependence; 4) Preexisting neurological disorders, dementia or previous stroke; 5) History of major head trauma; 6) Legal blindness or severe visual impairment; 7) history of psychosis or other Axis I disorder that is primary; 8) Life expectancy <1 yr.; 9) Severe arthritis or other problems that limit passive ROM; 10) History of DVT or pulmonary embolism within 6 months; 11) Uncontrolled diabetes with recent weight loss, diabetic coma, or frequent insulin reactions; 12) Severe hypertension with systolic >200 mmHg and diastolic >110 mmHg at rest; 13) attempt of suicide in the last 2 years or at suicidal risk assessed by SCID interview; 14) History of seizures or currently prescribed anti-seizure medications; 15) Current enrollment in a clinical trial to enhance motor recovery; 16) Pregnancy verified by urine pregnancy test.

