extremity muscle strength and power were accompanied by improvements in self-selected as well as fastest comfortable walking speeds. Specifically, strength increased by 25.0 and 23.3 percent in the paretic and non-paretic plantar flexor (PF) muscle groups, respectively. Improvements in knee extensor (KE) strength were not as large, with gains of 14.8 percent in the paretic side and 16.0 percent in the non-paretic side. Gains in KE peak power of 28.6 and 30.7 percent in the paretic and non-paretic limbs, respectively, were also found post-training. Self-selected walking speed increased from 0.71 to 0.92 m/s, exceeding the clinically meaningful difference reported for participants post-stroke. Fastest comfortable walking speed increased from 1.10 to 1.51 m/s.

POWER training improves depressive severity:

We have enrolled and trained 10 subjects to date with mild to moderate PSD in POWER training. We measured depression severity (HRSD), at pre-, mid- and post-training time points over the 12 week training period. HRSD scores prior to training (15.1 ± 7.5) decreased after 6 weeks (10.8 ± 4.3) and 12 weeks (8.5 ± 3.3) of training. In addition, 7 subjects realized a $>50\%$ reduction in depression severity (i.e. response) and 8 were considered to have achieved remission (i.e. HRSD < 10). Although we did not have a comparison group with PSD in this pilot study, these data suggest the potential for POWER training to positively impact depression severity in individuals with PSD.

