Assessment of depression severity: The Hamilton Rating Scale for Depression (HRSD) and the Montgomery- Åsberg Depression Rating Scale (MADRS) are the most widely used instruments for obtaining ratings of depressive symptoms. The HRSD samples a broader array of symptoms and is the primary outcome for this project. However, the MADRS is also sensitive to therapeutic change and includes more focus on vegetative symptoms. Thus, we will utilize a single structured interview that contains the questions necessary to complete both the HRSD and MADRS. The order of questions results in a more efficient interview, clustering material of similar content, thereby reducing repetition. Items that require patient observation (e.g., retardation, agitation) or spontaneous patient report (e.g., HRSD mood item) occur towards the end so scores are not contaminated by direct questioning on these topics. Items dealing with somatic symptoms (e.g., sleep) occur before items focusing on psychological state (e.g., guilt, suicide) so as to develop rapport during the earlier part of the interview leading to fuller disclosure of symptoms that are difficult to discuss. Critically, the rater administering the interviews will not be involved with any other aspects of the study. A trained psychiatry practitioner ([name] or one of his colleagues) will assess depression severity bi-weekly. Test-retest reliability for the HRSD is extremely high (0.94; 95% CI 0.89-0.97) and thus appropriate to use for repeated measure of depression severity.⁴¹ Depression will be classified as mild (HRSD = 12-16) or moderate (HRSD ≥ 17) and diagnosed upon enrollment using the Structured Clinical Interview for Depression (SCID) according to the Diagnostic & Statistical Manual of Mental Disorders, 4th Edition (DSM-IV).

Assessment of cortical excitability and neuroplastic potential via PAS: A means of testing “neuroplastic potential”, without dependence on subject motivation and effort (frequently impaired in depression) is via a non- invasive brain stimulation protocol called paired associative stimulation (PAS). PAS uses repeated, timed and paired peripheral nerve stimulation and TMS of the contralateral motor cortex and induces consistent changes in excitability of the motor cortex in healthy subjects as demonstrated by changes in the amplitude of MEPs.

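### Section 5.0 sets no HRSD total for entry and remission has no baseline condition, so a participant already below 10 could be counted as remitted without improving

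*Combined protocol and SAP*

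**What the plan says.** - **Entry (Section 5.0).** For the depressed group, "depressed subjects will screen for probable major depressive disorder (PHQ-9 > 10") and must "be diagnosed using the Structured Clinical Interview for Depression (SCID) according to the Diagnostic and Statistical Manual of Mental Disorders, Fourth Edition (DSM-IV"). The only HRSD requirement in the inclusion list is one item: "HRSD question #9 regarding suicide <2". The exclusion list contains no HRSD total either.
- **Population (Section 3.0).** "Chronic stroke survivors with mild to moderate depression (n=32) will be randomly assigned" to POWER or stretching.
- **Bands (Section 10.0).** "Depression will be classified as mild (HRSD = 12-16) or moderate (HRSD ≥ 17) and diagnosed upon enrollment". No band is given below 12, and the moderate band has no upper limit.
- **Remission (Section 12.0).** Remission is HRSD below 10 and response is a reduction of at least 50%. Both are reported as "rates following training and at a six-month follow-up". Remission carries no condition on the baseline score.
- **Hypothesis (Section 1.0).** Aim 1 expects higher response and remission rates with POWER.
- **Pilot (Section 2.0).** Ten people, also labelled mild to moderate, had "HRSD scores prior to training (15.1 ± 7.5").

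**The concern.** Entry is decided on PHQ-9 and SCID, while remission is decided on HRSD. The two are linked only by the bands in Section 10.0, which are worded as a classification. The plan does not say what happens to a person who passes both entry tests with an HRSD below 12. If such a person enters at 8 and is still at 8 after training, the rule in Section 12.0 records a remission although nothing changed.

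The remission comparison is at stake. People who are below 10 throughout add the same count to numerator and denominator in each arm, so both rates rise and the difference shrinks. With 16 per arm, a chance imbalance of one or two such people also moves a rate visibly: one person is 1/16, or about 6 percentage points.

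**Working it through.** The plan gives no figure for remission, so there is none to reproduce. Its one Aim 1 power figure does not use the remission rule. For completeness: the variance factor for the mean of 10 AR(1) measurements with correlation 0.5 is 0.260, so the SD is 5.3 × √0.260 = 2.70. With 13 per arm and a difference of 2.94, z = 2.94 / (2.70 × √(2/13)) − 1.96 = 0.81, a power of 79%. This agrees with the stated 80% and is unaffected by this point.

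**Step 1: the rules side by side.**

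| Section | Role | HRSD total required |
|---|---|---|
| 5.0 | Entry criteria | None |
| 3.0 with 10.0 | Description and classification | 12 or more, by implication |
| 12.0 | Remission | Below 10 at the later visit; baseline not mentioned |

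If 3.0 and 10.0 are enforced at entry, nobody starts below 10. If 5.0 alone operates, somebody can.

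**Step 2: what the pilot figures allow.** Inputs are n = 10, mean 15.1 (sum 151) and SD 7.5, with ± read as SD. I searched all sets of ten whole-number scores with sum 151 and SD between 7.45 and 7.55.
- If every score is 12 or more, at least one must be 36 or more.
- If every score is 10 or more, at least one must be 26 or more. An example is 10 five times, 11, 12, and 26 three times: sum 151, SD 7.55, which is 7.549 before rounding and so prints as 7.5.

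So the pilot contained either a score below 10 or a score of at least 26. The summary figures do not say which.

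**Step 3: how many could start below 10.** Suppose the trial recruits like the pilot (mean 15.1, SD 7.5).
- Normal: Φ((10 − 15.1)/7.5) = Φ(−0.68) = 0.248. With a correction for whole-number scores, Φ((9.5 − 15.1)/7.5) = Φ(−0.747) = 0.228.
- Gamma with the same mean and SD: 0.273. Lognormal: 0.260.
- Times 32: 0.228 × 32 = 7.3 and 0.273 × 32 = 8.7, so 7 to 9 people.

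With smaller SDs and a normal shape, the share falls. It is 15-17% at SD 5.3 (the planning value in Section 12.0) and 4-6% at SD 3.3 (the pilot's week-12 value, used only to show the range). If the bands are enforced it is 0. The overall range is therefore 0 to about 27%.

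**Step 4: effect on the contrast.** Let a share p in each arm start and stay below 10, and let D be the remission difference among the rest. The observed difference is (1 − p) × D. At p = 0.27 it is 0.73 × D, a loss of about a quarter. At p = 0 there is no loss.

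**The case against.** The strongest reply is that Sections 3.0 and 10.0 together already imply a floor of 12, above the remission cut-off. If staff apply those bands at enrollment, the problem does not arise. That stands as far as it goes, and it is why the point is conditional. It does not close the gap, because the list that decides entry omits the band and Section 10.0 does not say that a lower score excludes anyone.

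Four stronger readings are tempting, and the documents do not support them.
- **The pilot proves that people outside the band were recruited.** A reader might note that scores confined to 12-22 with mean 15.1 have an SD of at most √(3.1 × 6.9 × 10/9) = 4.9. But 22 comes from the referral trigger in Section 15.0. It is not part of the moderate band, which is open-ended. The example in Step 2 shows that the pilot figures can arise with nobody below 10.
- **Seven to nine people is the expected number.** It is the top of the range. The plan does not say that the pilot screened on PHQ-9 and SCID, so its lower tail may not carry over.
- **Response is inflated too.** Response is measured relative to baseline, so a low starting score does not confer it.
- **Anyone below 10 at baseline is a remitter by definition.** Remission is judged on the later score; a person at 9 who rises to 11 is not counted.

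It is also fair to say that remission is not the primary outcome, that randomisation tends to balance such people between arms, and that Section 12.0 plans a secondary adjustment for depression level. These points limit the harm to dilution and chance imbalance in a secondary comparison. The adjustment does not change who is counted as remitted.

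**Conclusion.** The concern holds in conditional form. Section 5.0 has no explicit HRSD total, the bands in Sections 3.0 and 10.0 are not made an entry rule, and the remission rule ignores baseline. Unless the bands are enforced at entry, a participant already below 10 could be counted as remitted without improving. The consequence is a higher remission rate in both arms and a between-arm difference smaller by between nothing and about a quarter. This rests on three assumptions: the pilot's ± is an SD, the baseline shape is normal, gamma or lognormal, and those who start below 10 stay there. The primary HRSD comparison's stated power and the response definition are not in question. The point should be settled before analysis, but it does not threaten the trial's main comparison.

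**What to change.** 1. **Section 12.0.** State that remission is counted only among randomised participants with baseline HRSD of 10 or more, and that those below 10 at baseline are reported separately by arm. Provided the baseline score is taken before assignment, this subset is fixed in advance and the randomised comparison is kept.
2. **Sections 3.0, 5.0 and 10.0.** Reconcile the entry criteria for depressed participants with the HRSD bands that describe the population, and say what happens to a person who passes PHQ-9 and SCID but scores below the mild band. Which clinical threshold applies is for the investigators to decide.

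The cost in text is one analysis sentence and one reconciled criterion. The cost in numbers is the remission denominator. In the worst case 32 falls by about 9 to 23, a loss of about a quarter, which is material in a trial this size. If the bands are enforced, nobody is removed and the first change serves only as a safeguard.
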